**Table 2: cGVHD Response Definitions**

Response	Definition
Complete Response (CR)	Resolution of all manifestations of cGVHD in each organ or site
Partial Response (PR)	Improvement in at least one organ or site without progression in any other organ or site
Lack of Response (LR)	
Mixed (LR-M) *	Complete or partial response in at least one organ accompanied by progression in another organ
Unchanged (LR-U)	Outcomes that do not meet the criteria for complete response, partial response, progression or mixed response
Progression (LR-P)	Progression in at least one organ or site without a response in any other organ or site

\* Considered progression for purposes of analysis

### 3.8.2 Secondary Efficacy Endpoints

#### 3.8.2.1 Duration of Response (DOR)

The primary definition of DOR is the time from first documentation of response to the time of first documentation of deterioration from best response (e.g., CR to PR, or PR to LR).

The secondary definition of DOR is the time from first documentation of response to the time of first documentation of lack of response.

The tertiary definition of DOR is the time from first documentation of response to the time of initiation of new systemic cGVHD therapy.

The quaternary definition of DOR is the time from first documentation of response to the time of first documentation of lack of response (as the secondary definition) but with durations summed for multiple response/lack of response episodes.

The DOR will be reported only for responders and statistics will include:

- Kaplan-Meier plots and descriptive statistics of DOR. The censoring rules in [Table 3](#) will be applied
- Landmark analyses: Number and percentage of subjects with response sustained for  $\geq 12$ ,  $\geq 20$ ,  $\geq 24$ ,  $\geq 32$ ,  $\geq 36$ , and  $\geq 48$  weeks

**Table 3. Censoring Rules for Duration of Response**

DOR	Events	Censoring
Primary	

• Deterioration from best response

• Initiation of new systemic therapy for cGVHD

• Death

	

• Last documented response assessment

• If LR or initiation of new systemic therapy happens immediately after two or more missed response assessments, the event date should be set as four weeks (one cycle) after last documented response assessment prior this event

Secondary	

• Documented LR

• Initiation of new systemic therapy for cGVHD

• Death

	

• Last response assessment or long term follow up assessment, whichever is the latest and available

Tertiary	

• Initiation of new systemic therapy for cGVHD

• Death

	

• Same with censoring rule for primary and secondary

Quaternary	

• Documented LR

• Initiation of new systemic therapy for cGVHD

• Death

 
With summation of DOR from multiple episodes
	

cGVHD = chronic graft versus host disease; DOR = duration of response; LR = lack of response

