Participants will receive belumosudil treatment in 28-day cycles until clinically significant progression of cGVHD (defined as progression requiring addition of new systemic therapy for cGVHD), histologic recurrence of underlying malignancy, unacceptable toxicity, Investigator decision, participant preference / withdrawal of consent, lost to follow-up, sponsor decision, or death (whichever occurs first).

Participants who experience cGVHD progression as defined by NIH criteria but for whom no new systemic therapy is planned may continue to receive belumosudil and be assessed again at their next cycle. If progression per NIH criteria is not confirmed or no new systemic therapy is planned, participants may continue on belumosudil per investigator discretion until they fulfill one of the criteria requiring discontinuation of study drug.

Under Protocol Amendment 3, all participants (excluding the 20 adolescent participants) that have received at least 6 months of belumosudil treatment or are in long-term follow-up without having a failure-free survival event are expected to end participation in study KD025-213. Participants may continue to participate in study KD025-213 if the Investigative Site is awaiting IRB approval of the KD025-217 rollover study titled: “Extended Treatment and Follow-up of Participants Treated with Belumosudil in Study KD025-208 or Study KD025-213”.

The primary endpoint is the overall response rate (ORR), defined as the proportion of participants achieving a partial response (PR) or a complete response (CR) as defined by the 2014 NIH Consensus Development Project on Clinical Trials in cGVHD ([Appendix B](#)). Response criteria will be assessed after Cycles 1, 2, 3 and 4 and then after every other Cycle thereafter (Day 1 of Cycles 2, 3, 4, 5, 7, 9, 11, etc.) ([Table 6](#)). Following Protocol Amendment 5, in adolescent participants still to be enrolled, response criteria will be assessed after Cycles 1, 2, 4, and 6 and then after every third cycle (Day 1 of cycles 2, 3, 5, 7, 10, 13, etc.). Responses are assessed with respect to baseline.

Analyses of the primary endpoint will be participant to multiplicity adjustment per a Hochberg procedure ([Section 11.2.1](#)).

Secondary endpoints will include assessments to evaluate the clinical meaningfulness of responses. These include duration of response, changes in Lee Symptom Scale Scores, response by organ system and changes in corticosteroid dosage.

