6.2.8 Long-Term Follow-Up

After the follow-up visit is completed, participants will be contacted approximately every 12 weeks eg, by telephone, e-mail, or postal mail until a failure-free survival event occurs or until the study close-out (whichever occurs first) to confirm survival status, any changes in treatment for cGVHD and the initiation of treatment for the underlying disease. Alternatively, this information may be derived from medical records.

With Protocol Amendment 3, all participants that have not yet had a failure free survival event will end participation with KD025-213. Participants may continue to participate in KD025-213 if the Investigative Site is awaiting IRB approval of the KD025-217 rollover study titled: "Extended Treatment and Follow-up of Participants Treated with Belumosudil in Study KD025-208 or Study KD025-213".

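### Primary DOR counts failures found in follow-up as events but censors event-free responders at their last response assessment, so late DOR tends to be understated; the 4-week re-dating rule does not fit 8-week visits

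*SAP*

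**What the plan says.** SAP Table 3 (Censoring Rules for Duration of Response) lists three primary DOR events: deterioration from best response, "Initiation of new systemic therapy for cGVHD", and death. None is limited to the treatment period. The censoring date is "Last documented response assessment". The same cell adds a dating rule: "If LR or initiation of new systemic therapy happens immediately after two or more missed response assessments", then "the event date should be set as four weeks (one cycle) after last documented response assessment prior this event". Death is not mentioned in that rule.

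Elsewhere the table prints a different censoring date: "Last response assessment or long term follow up assessment, whichever is the latest and available". It appears in the Secondary row, but the cells look merged and the alignment is uncertain. The primary rule is the same on either reading.

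In the schedule of assessments (Protocol Appendix A) the last response assessment is at EOT. Under Protocol 6.2.8, after the follow-up visit "participants will be contacted approximately every 12 weeks", by various means, "to confirm survival status, any changes in treatment for cGVHD and the initiation of treatment for the underlying disease". Response is not assessed at these contacts.

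Protocol 3.1 places response assessments after Cycles 1 to 4 "and then after every other Cycle thereafter". They are therefore 4 weeks apart up to C5D1 and 8 weeks apart from then on, and SAP 3.8.2.2 gives the same schedule for the Lee Symptom Scale. Amendment 5 moves to Day 1 of Cycles 2, 3, 5, 7, 10 and 13. Section 3.1 limits that to adolescents still to be enrolled, while section 6.2.4 states it without the limit.

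**The concern.** Take two responders who stop drug while still responding. If follow-up finds new therapy or death in the first, that is an event on its date. If follow-up finds nothing in the second, that person is censored back at EOT, and the event-free follow-up time is discarded. Whether someone is censored early therefore depends on what happens to them later, which Kaplan-Meier does not allow.

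Such responders are expected. Protocol 4.8.1 lists adverse events, investigator decision and voluntary discontinuation as reasons to stop, and section 5.2.1 allows taper to discontinuation after a sustained response.

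The dating rule is a second, separate problem. One cycle is the visit interval only early in treatment.

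DOR carries descriptive weight. Protocol 3.1 lists it first among the endpoints meant to show that responses are clinically meaningful, and section 11.2.1 bases the 12-month analysis on more mature DOR data. Late DOR is where the distortion falls.

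**Working it through.** The documents give no DOR median, event count or power, so there is no stated figure to reproduce.

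**1. Risk set.** At a follow-up event time let d be the events, n the responders still under response assessment, k those off drug who will later fail, and m all those off drug and event-free so far (m ≥ k). Table 3 uses the hazard increment d/(n + k). With everyone followed to last contact it would be d/(n + m). Since k ≤ m, the increment is too large whenever some off-drug responders do not fail.

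**2. Dating rule.** Lack of response (LR) found at the first visit after two missed visits, in weeks from the last assessment:

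| Visit spacing | First missed visit | LR found | Rule gives | Rule minus first missed visit |
|---|---|---|---|---|
| 4 | 4 | 12 | 4 | 0 |
| 8 | 8 | 24 | 4 | −4 |
| 12 | 12 | 36 | 4 | −8 |

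Example on the original schedule: response at week 8, last assessment at C7D1 (week 24), C9 (week 32) and C11 missed, LR at C13. The rule gives 24 + 4 − 8 = 20 weeks. Dating at the first missed visit gives 32 − 8 = 24 weeks. The ≥24-week landmark in SAP 3.8.2.1 changes.

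**3. Size at 48 weeks, first assumption set.** Assumed, not from the documents: on-drug loss of response with mean 60 weeks (λ = 1/60); stopping for other reasons with mean 40 or 80 (a); new therapy with mean 40 or 80 after stopping (b); 8-week visits; follow-up 26 to 78 weeks. The Table 3 value is a simulated Kaplan-Meier estimate. The true DOR has a closed form:

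- Response lost off drug at the same rate: S(t) = e^(−λt) × (a·e^(−bt) − b·e^(−at))/(a − b), or e^(−λt)(1 + at)e^(−at) when a = b.
- Response never lost off drug: S(t) = e^(−(λ+a)t) + a[e^(−bt) − e^(−(λ+a)t)]/(λ + a − b).

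For 40/40 at t = 48 the first is 0.449 × 2.2 × 0.301 = 0.298. The second is 0.135 + 0.025 × (0.301 − 0.135)/0.01667 = 0.384.

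| Stop / therapy mean | Table 3 (%) | True, lost off drug | Error | True, not lost | Error |
|---|---|---|---|---|---|
| 40/40 | 25.9 | 29.8 | −3.9 | 38.4 | −12.5 |
| 40/80 | 31.2 | 35.8 | −4.6 | 49.0 | −17.8 |
| 80/40 | 34.8 | 35.8 | −1.0 | 41.0 | −6.2 |
| 80/80 | 37.5 | 39.5 | −2.0 | 47.3 | −9.8 |

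A rerun of these scenarios at 24 weeks gives errors of −0.4 to +1.1 points in the first case and about −2 to −7 in the second.

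**4. Second assumption set, response can be lost off drug.** Simulation of 100,000 responders per scenario. Assumed medians: deterioration 52 or 104 weeks; stopping 26, 52 or 104; new therapy or death 104 or 208, with the hazard multiplied by 1, 2 or 4 after stopping. Missed visits 0% or 10%; cut-off 28 to 104 weeks after response. Against the truth, Table 3 is off by −5.4 to +0.2 points at 48 weeks, −0.3 to +4.6 at 24 weeks, and −11.6 to +2.8 weeks for the median. The upward errors arise because deterioration is seen only at visits.

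One slice (original schedule; medians 104, 52 and 208), 48-week DOR in % with error in points:

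| Hazard after stopping | Truth | Table 3 | Matched 28-day window | All events, last-contact censoring | Table 3 with post-EOT visits read as missed |
|---|---|---|---|---|---|
| ×1 | 61.9 | 58.5 (−3.4) | 60.7 (−1.2) | 68.5 (+6.6) | 56.0 (−5.9) |
| ×2 | 59.5 | 56.3 (−3.2) | 60.2 (+0.7) | 65.4 (+5.9) | 52.2 (−7.3) |
| ×4 | 55.3 | 52.7 (−2.6) | 59.1 (+3.8) | 59.7 (+4.4) | 46.4 (−8.9) |

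Over all scenarios the matched window (therapy and death counted to 28 days after stopping, everyone else censored at the last assessment) is off by −4 to +5 points. Last-contact censoring is 1 to 16 points above the truth.

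**5. The 4-week rule alone.** Removing it changes the estimate by at most 0.6 points at 24 weeks and 0.2 at 48 weeks, because under 1% of responders are re-dated at 10% missed visits. If visits not scheduled after EOT are read as missed, the estimate falls a further 3 to 11 points at 24 weeks and 2 to 7 at 48 weeks.

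**The case against.** - **Inference from the event list.** The SAP does not say that events found in follow-up count; this follows only because the list has no limit. The wording stands as the rule a programmer would apply.
- **Weight of the endpoint.** DOR is descriptive with no alpha (SAP 3.2), ORR does not depend on it, and shorter DOR is conservative for the drug. All of this stands.
- **Other analyses.** There are three further DOR definitions, and TTNT and FFS use follow-up for censoring. They lessen the harm but do not repair the primary definition.
- **The gap rule.** On the plain reading nothing is scheduled after EOT, so nothing can be missed there and the rule hardly matters. That stands for size. The SAP does not define a missed assessment, so two programmers could still produce different curves.

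Some stronger readings are tempting. A reader might compare Table 3 with simply censoring at the last assessment (39.8 to 43.7% in the first assumption set) and infer 6 to 14 points of bias, or 7 to 18 with re-dating of off-drug events. That compares two estimators. The benchmark drops therapy and death after stopping, which Protocol 11.7.2 defines as DOR events. A reader might also infer that visits are 12 weeks apart for everyone; that spacing exists only under Amendment 5, and section 3.1 restricts it. Nor is the bias uniformly downward: at 24 weeks late detection can offset or exceed it.

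**Conclusion.** The mismatch between events and censoring is real and tends to understate late primary DOR. If response can also be lost off drug, the understatement is about 0 to 5 points at 48 weeks, with little effect at 24 weeks. If response is never lost off drug, it is about 6 to 18 points at 48 weeks in the scenarios tried. The documents give no data to choose between these cases, and every rate used is assumed.

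The 4-week rule is inconsistent with the schedule wherever visits are 8 weeks apart, overwrites known therapy dates and leaves out death. Its numerical effect is under 1 point unless post-EOT visits are treated as missed. The documents do not support extending any of this to the ORR conclusion.

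**What to change.** In SAP Table 3, for primary DOR:

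1. Use one horizon for events and censoring. Count new therapy or death only up to a stated short window after the last response assessment, such as the 28-day follow-up; otherwise censor at that assessment. Word the window so that deaths on drug between 8-week visits still count; the version checked above ran to 28 days after stopping drug.
2. State that visits not scheduled after EOT are not missed assessments.
3. Replace the 4-week date with the actual date for new therapy and death, and with the first missed scheduled assessment for LR.
4. Add a sensitivity analysis with all events on their actual dates and event-free responders censored at last contact. Report it as an upper bound, because response is not assessed in follow-up. It should not replace the primary rule.

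The matched window removes censoring that depends on the future outcome. It does not remove all bias: where the hazard rises sharply after stopping, its estimate can be up to about 5 points high and can even exceed the sensitivity estimate.

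Cost: SAP wording and reprogramming, no new data. Later known therapies and deaths leave the primary DOR and appear only in the sensitivity analysis, TTNT and FFS. The SAP history ties the DOR definitions to a regulatory meeting, so the change should be documented against that. For analyses already reported it would be a supplementary re-analysis.

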### 3.8.2.2 Lee Symptom Scale Score (LSS)

Lee cGVHD Symptom Scale (see questionnaire in Protocol Appendix D) will be assessed on Day 1 of Cycles 2-5, then on Day 1 of every other Cycle thereafter and EOT. The questionnaire consists 30 items of 7 domains: skin, eyes and mouth, breathing, eating and digestion, muscles and joints, energy, and mental and emotional. Each question is scored 0, 1, 2, 3 or 4.

A domain score will be calculated for each domain by taking the mean of all items completed if more than 50% were answered and normalizing to a 0 to 100 scale. A summary score will be calculated as average of all nonmissing domain scores if more than 50% of them are nonmissing. A higher score indicated more bothersome symptoms. 7 points difference on the summary score of cGVHD symptom scale was found to be clinically meaningful.

$$\text{Raw Score} = \frac{I_1 + \dots + I_m}{m}, \quad \text{Domain Score} = (\text{Raw Score} / 4) * 100$$

$$\text{Summary Score} = \frac{\text{Domain Score}_1 + \dots + \text{Domain Score}_n}{n}$$

In the above formulas, m is the number of items have nonmissing value in a domain, and n is the number of domains have nonmissing domain scores.

Analyses will include:

- Both score and change-from-baseline values (summary score and domain scores) will be summarized as continuous variables by visit
- Number and percent of subjects with a  $\geq 7$ -point reduction (7-PtR) from baseline (C1D1)
- Number and percent of subjects with a 7-PtR from baseline on 2 consecutive assessments
- Duration of a 7-PtR (DO7-PtR) (defined as time from documentation of the first  $\geq 7$ -point reduction to the first documentation of less than 7-point reduction). If there are multiple episodes, then DO7-PtR will be measured as the sum of DO7-PtR from all episodes.

These analyses will be performed on mITT, responder and nonresponder populations. 7-PtR and DO7-PtR will be censored after new systemic cGVHD treatment.

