11.7.2 Secondary Efficacy Endpoints

Secondary endpoints are as follows:

- Duration of response (DOR): Assessments of DOR will include:
 - The time from initial response of PR or CR until documented progression from best response of cGVHD, new cGVHD therapy, or death.
 - Time from initial response to start of additional systemic cGVHD therapy or death.
- Changes in the Lee Symptom Scale Score: Analyses will include:
 - Number of participants with a ≥ 7 point reduction.
 - Number of participants with a ≥ 7 point reduction on 2 consecutive assessments.
 - Duration of a ≥ 7 point reduction.
- Response by organ system: The response assessment for the nine individual organs (Skin, Eyes, Mouth, Esophagus, Upper GI, Lower GI, Liver, Lungs, and Joints and fascia).
- Time to response (TTR): defined as the time from the first dose of belumosudil to the first documented cGVHD response.
- Time to next therapy (TTNT): defined as the time from the first dose of belumosudil to the start of additional systemic cGVHD therapy.
- Number and percentage of participants who have a best response of PR and number and percentage of participants who have a best response of CR.
- Change in corticosteroid dose:
 - The prednisone equivalent dose of corticosteroids (mg/kg/day) during the study will be analyzed ([Appendix K](#)).
- Change in calcineurin inhibitor dose.
- Failure-free-survival (FFS): FFS is defined as the absence of cGVHD treatment change, non-relapse mortality and recurrent malignancy ([Section 6.3.5](#)). Median FFS (from first dose of belumosudil) and landmark FFS at 1 year will be analyzed.
- Overall survival (OS): Defined as time from first dose of belumosudil to the date of death due to any cause.
- Changes in cGVHD global severity rating using the Clinician-Reported Global cGVHD Activity Assessment.

- Changes in symptom activity using the cGVHD Activity Assessment Patient Self-Report.

Descriptive statistics will be provided for all secondary endpoints.

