### **Handling of Incomplete or Missing Data**

Missing data will not be imputed in general and it will be reported as missing in all listings. For categorical variables, patients with missing data are not included in calculations of percentages unless otherwise specified.

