**Table 4: Efficacy TLFs**

T/L/F	Title	Population
Primary Endpoint: ORR		
T	Overall Response Rate*	miITT
T	Overall response rate (ORR) for responses occurring within 6 months of treatment	miITT
T	Overall response rate (ORR) for responses occurring within 12 months of treatment	miITT
T	Landmark ORR at 6 months	miITT
T	Landmark ORR at 12 months	miITT
F	Forest plot of ORRs (1. all subjects in an arm, subgroups within arm; 2. Two arm combined if ORRs of those two arms are similar)	miITT

 In all tables, figures and listing, results will be presented by two treatment arms and overall, unless otherwise specified.

T/L/F	Title	Population
L	Listing of overall response by subject by visit	miITT
Secondary Endpoint: DOR		
T	Descriptive Kaplan-Meier and landmark (12, 20, 24, 32, 36, 48 weeks) statistics for DOR*	Responder
F	Kaplan-Meier plot of DOR*	Responder
L	Listing of all DOR episodes for each subject	Responder
Secondary Endpoint: TTR		
T	Descriptive statistics for cumulative response rate over time (TTR)	Responder
F	Cumulative response rate over time (TTR)	Responder
L	Listing of TTR for each subject	Responder
Secondary Endpoint: LSS score		
T	Descriptive statistics for LSS score for: a) number of subjects with a 7-PtR from baseline; b) number of subjects with 7-PtR on 2 consecutive assessments; c) DO7-PtR (<8, 8-16, 16-24, 24-32, 32-40, 40-48, >48 weeks)	miITT, Responder, Nonresponder
T	Summary of LSS Score (overall and each of seven domains) raw and change from baseline by visit	miITT, Responder, Nonresponder
F	Summary of Lee Symptom Scale Score (overall and each of seven domains) raw and change from baseline by visit	miITT, Responder, Nonresponder
L	Listing of Lee Symptom Scale Score by subject, domain and visit	miITT
Secondary Endpoint: Response by Organ System		
T	Best response by individual organ	miITT
T	Organ responses according to baseline NIH / severity score	miITT
L	Listing of organ score and response assessment by subject and visit	miITT
T	Descriptive statistics for cumulative response rate over time (TTR) by organ	miITT, Responder
F	Cumulative response rate over time (TTR) by organ	miITT, Responder
Secondary Endpoint: Corticosteroid Dose		

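### The SAP has no rule for a 7-point Lee reduction still ongoing at the last assessment, and the planned duration bands cannot use censored times, so reported durations are biased downward or at best unchanged

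*SAP*

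**What the plan says.** Protocol 11.7.2, under "Changes in the Lee Symptom Scale Score: Analyses will include", lists the duration of a reduction of at least 7 points and gives no further rule.

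SAP 3.8.2.2 supplies the definition. The clock starts at the first documented reduction of at least 7 points and runs "to the first documentation of less than 7-point reduction". With several episodes, "DO7-PtR will be measured as the sum of DO7-PtR from all episodes". The one censoring statement is that "7-PtR and DO7-PtR will be censored after new systemic cGVHD treatment". The section names no estimation method for the duration.

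SAP Appendix A, Table 4 (Efficacy TLFs) plans a table of descriptive statistics, with the duration laid out as "DO7-PtR (<8, 8-16, 16-24, 24-32, 32-40, 40-48, >48 weeks", for the mITT, responder and nonresponder populations. It lists no Kaplan-Meier table or figure for this endpoint. The general rule in SAP 3.14 is that "Missing data will not be imputed in general and it will be reported as missing in all listings".

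Duration of response is treated differently. SAP 3.8.2.1 plans "Kaplan-Meier plots and descriptive statistics of DOR", and its censoring table (Table 3) uses "Last documented response assessment" for responders with no event. The same table counts new systemic therapy and death as events. TTNT and FFS (SAP 3.8.2.5 and 3.8.2.8) also have a last-assessment censoring date and Kaplan-Meier output.

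**The concern.** The definition needs a documented loss. A participant whose last Lee score still shows the reduction has none, whether follow-up stopped at the data cut, at withdrawal, at death or at rollover. These are the people with the longest benefit. If the programmer gives them no value, the table describes only those who lost the benefit. If the programmer stops the clock at the last visit, an unfinished duration goes into a band as though it were complete. Two programmers working from the same text could produce different tables.

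This endpoint is the Lee analysis that speaks to durability of symptom benefit, and its upper bands suffer most. It is also split by responder status. If responders stay improved longer, which is plausible but not stated, the distortion differs between the two groups.

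**Working it through.** **Two records under the SAP text.** The SAP's Lee schedule (Day 1 of Cycles 2-5, then every other cycle) puts visits at weeks 4, 8, 12, 16, 24 and every 8 weeks after that.

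- Record 1: baseline 30, then 20, 19, 18, 18, 17. The reductions are 10, 11, 12, 12, 13, all at least 7. No loss is documented, so no duration is defined. Cut at week 24, it is 24 - 4 = 20 weeks and goes into the 16-24 band as if finished.
- Record 2: baseline 30, then 20 at week 4 and 27 at week 8. The reductions are 10 and 3. The duration is 8 - 4 = 4 weeks, fully defined.

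The brief improver is counted. The sustained one is missing or shortened.

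**Reach of the bands at the primary analysis.** This analysis comes about 6 months, or 26 weeks, after the 126th mITT participant (SAP 3). The earliest Lee reduction is at week 4, so the last participants enrolled can show at most 26 - 4 = 22 weeks. The four bands from 24-32 upward are closed to them, whatever their true benefit.

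**Size.** The documents give no figure to reproduce, so this is an illustration. Assumptions not in the documents:

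- one episode per person and exponential duration;
- first reduction at week 4, 8, 12 or 16 (weeks 4, 8 or 12 in the rows marked *);
- last assessment opportunity uniform over the range shown, with only that cut-off ending observation.

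Accrual of 12 months (the figure before Amendment 2) gives 6-18 months of follow-up at the primary analysis and 12-24 months at the follow-up analysis. Accrual of 24 months (Protocol 3.3, for the enlarged trial) gives 6-30 months at the primary analysis.

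For an assumed median of 24 weeks, P(duration > 48) = 0.5^(48/24) = 25%. A loss is documented only at the next visit, so the share with full follow-up is slightly higher, at 26-27%, and the documented median is 28 weeks.

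| Follow-up | Still improved | Median: dropped / cut / full (weeks) | Over 48 weeks: dropped / cut / full |
|---|---|---|---|
| 6-18 months | 37% | 16 / 20 / 28 | 3% / 7% / 27% |
| 6-30 months | 23% | 20 / 24 / 28 | 13% / 17% / 26% |
| 12-24 months | 18% | 24 / 28 / 28 | 12% / 20% / 26% |
| about 6 months for all | 67% | 8 / 12 / 28 | 0% / 0% / 27% |
| 24-72 weeks* | 38% | 16 / 20 / 28 | 2-3% / 6% / 27% |
| 24-128 weeks* | | | 14% / 17% / 27% |
| 48-96 weeks* | | | 11% / 20% / 27% |
| 48-152 weeks* | | 24 / - / 28 | 18% / 24% / 27% |

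Other true medians at 6-18 months of follow-up:

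- Assumed 16 weeks: 24% still improved; medians 16 / 16 / 20; over 48 weeks 2% / 4% / 14%.
- Assumed 48 weeks: 59% still improved; medians 20 / 28 / 52; over 48 weeks 6% / 14% / 52%.

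At 12-24 months with an assumed median of 16 weeks, the median is 20 under every reading, so it does not move there.

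**Kaplan-Meier.** S(t) is the product over loss times up to t of (1 - d/n), where d is the number losing the reduction and n the number still at risk; ongoing participants leave the risk set at their last Lee visit. At 6-18 months this gives medians of 20, 28 and 48 weeks for assumed medians of 16, 24 and 48, against 20, 28 and 52 with full follow-up. With about 6 months for everyone it gives 20 for an assumed 16, and correctly reports the median as not reached for 24 and 48.

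**Censoring at new therapy.** Suppose 20% or 40% of losses come with new systemic therapy before the next Lee visit (assumed median 24 weeks, follow-up 24-72 weeks*). Kaplan-Meier with censoring at new therapy then gives 32% or 42% at 48 weeks, against 27%. That error runs in the drug's favour, so the choice between event and censoring matters.

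**The case against.** A reader might infer that the SAP excludes sustained improvers or says they have no value. It does not. It states neither handling of an ongoing episode, and it does contemplate censored values, since it censors after new systemic treatment. What stands is narrower: that sentence covers only those who start new therapy, gives no date, and names no method that uses a censored time. Elsewhere (SAP 3.8.1) the SAP uses the same word for setting a response to non-response.

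The consequence is limited. The endpoint is descriptive and carries no alpha. The 7-point rate, the rate on two consecutive assessments, and the scores by visit do not use the disputed rule. The bias runs against the drug, so it cannot create a false claim of durability. All of this stands, and it is why the point is a recommended change and not a critical one.

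Protocol 11.2.1 presents the 12-month analysis as having more mature data for DOR and other endpoints. That reduces the problem without removing it: under the 12-24 month assumption the over-48-week band still shows 12% or 20% against 26%. A reader might take the 6-18 month figures as the size of the error, but they describe the less mature setting only.

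Finally, the sponsor chose total time improved, summed over episodes, which is reasonable for a fluctuating score. A first-episode analysis is a different quantity and should not displace the sum without saying so. That stands and shapes the fix.

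**Conclusion.** The gap is real. SAP 3.8.2.2 gives no end or censoring rule for a reduction ongoing at the last Lee assessment, the DOR censoring table is titled for DOR and does not reach this endpoint, and a table of duration bands cannot use a censored time. Either literal reading biases durations downward or leaves them unchanged.

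For an assumed 24-week median, and leaving aside the extreme case where everyone has about 6 months of follow-up, the over-48-week share is about 3% to 18% (dropped) or 6% to 24% (cut), against about 27%. The error is largest at the 6-month primary analysis and for the longest benefits. These sizes rest on the assumptions listed and on the SAP's visit schedule. Protocol 6.2.4 and 6.3.3.1 give different Lee schedules, which would shift when a loss can be documented.

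A reader might infer that the primary result is in doubt. It is not: ORR does not use this variable.

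**What to change.** In SAP 3.8.2.2, add a Kaplan-Meier analysis of time from the first documented 7-point reduction to the first documented loss:

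- Censor reductions still ongoing at the last Lee assessment.
- Count death and new systemic cGVHD therapy as events, in line with the SAP's DOR table.
- Run the SAP's stated censoring at new therapy as a sensitivity analysis.

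In Appendix A, Table 4, give Kaplan-Meier estimates at 8, 16, 24, 32, 40 and 48 weeks in place of the bands as the main durability summary. Keep the pre-specified summed multi-episode duration as a separate summary, and show how many participants were still improved at their last assessment.

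The cost is SAP wording and one changed table, with no new data. The downside is that first-episode duration and summed time are different quantities, so both must be labelled clearly.
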